Abbreviations: CGADR = Clinical Global Assessment of Discharge Readiness; CGI-S = Clinical Global Impression – Severity; C-SSRS = Columbia Suicide Severity Rating Scale; ECG = electrocardiogram; EQ-5D-5L= EuroQol-5D, 5-level; HbA1C = glycosylated hemoglobin; HVLT-R = Hopkins Verbal Learning Test-Revised; ICF = informed consent form; MADRS = Montgomery-Asberg Depression Rating Scale; MAGDA = Magda Avatar Game Depression Implicit Association Scale; MOAA/S = Modified Observer's Assessment of Alertness/Sedation; PHQ-9 = Patient Health Questionnaire – 9; SDS = Sheehan Disability Scale; C-SSRS = Columbia Suicide Severity Rating Scale; QLDS = Quality of Life in Depression Scale

Note: On intranasal dosing days, time 0 is defined as the time of the first intranasal spray. Therefore, postdose time points are referenced from this.

- a) If a subject withdraws before the end of the induction phase (ie, Visit 1.9, Day 28) for reasons other than withdrawal of consent, an “Early Withdrawal” visit (refer to Time and Events Schedule: Optimization/Maintenance Phase) should be conducted within 1 week of the last dose of esketamine nasal spray. If the early withdrawal visit is conducted on the same day as a scheduled visit, duplicate assessments are not required. Subjects who are currently in the induction phase at the time the 54135419TRD3008 study is completed will conduct an “End of Study” visit as their final study visit within 1 week of the last dose of esketamine nasal spray.
- b) There is no maximum time limit between completing the prior study and enrolling into 54135419TRD3008. If a study procedure from the prior study has already been performed on the same day, duplicate predose assessments do not need to be repeated on Visit 1.1 (Day 1) of 54135419TRD3008 study.
- c) Predose (if/when performed on intranasal dosing days).
- d) Postdose vital signs will be performed at 40 minutes, 1 hour, and 1.5 hours postdose. Please refer to Section 6.1 for guidance on blood pressure monitoring on intranasal dosing days.
- e) Twelve-lead ECG will be performed predose and t=1 hour postdose at Visit 1.1. Twelve-lead ECG will be performed at t=1 hour postdose only, at Visits 1.5 and 1.8. A time window of ±15 minutes will be permitted.

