Study Procedures												
Screening/Administrative												
Informed consent (prior to any procedure; except subjects entering phase from 54135419TRD3008 Induction Phase)	X											
Inclusion/exclusion criteria (predose; except subjects entering phase from 54135419TRD3008 Induction Phase)	X											
Study Drug												
Esketamine nasal spray treatment session ^{f),t)}	X	X ^{g)}	X	X ^{g)}		X ^{h)}						
Adjustment of intranasal treatment session frequency (if applicable) based on CGI-S				X		X	X					
Drug accountability (intranasal study medication)	X	X ⁱ⁾	X	X ⁱ⁾		X ⁱ⁾						
Efficacy Assessments (Clinician)^{j)}												
MADRS	X		X				X				X	
CGI-S	X	X	X	X		X					X	
Subject-Completed Assessments^{j)}												
PHQ-9	X		X						X		X	
SDS	X		X						X		X	
EQ-5D-5L	X		X						X		X	
TSQM-9	X								X		X	
QLDS ^{r)}	X		X						X		X	
Patient Stated-choice Preference Survey ^{k)}				X ^{l)}							X ^{l)}	
Safety Assessments (Clinician)												
Physical examination, weight	X								X ^{l)}		X	
Vital signs (predose): blood pressure, pulse, respiratory rate, and temperature	X	X ^{l)}	X	X ^{l)}	X ^{l)}							
Vital signs (postdose): blood pressure, pulse, and respiratory rate only ^{m)}	X	X ^{l)}	X	X ^{l)}	X ^{l)}							
12-lead electrocardiogram ⁿ⁾	X						X				X	
CSSRS ^{o)}	X	X ^{l)}	X	X ^{l)}		X					X	
MOAA/S ^{o)}	X	X ^{l)}	X	X ^{l)}								

Phase	Optimization/Maintenance Phase											Early Withdrawal/ End of Study ^{e)}
	Visit Number	2.1 ^{b),c)}	2.2	2.3	2.4	2.5 to 2.X						
	Study procedure frequency (following Week 4) through end of phase											
Week	1	2	3	4	5, 6, 7, 8, etc	6, 8, 10, etc	8, 12, 16, etc	12, 20, 28, etc	16, 28, 40 etc	28, 52, 76, etc		
Day	1	8	15	22	Every week	Every 2 Weeks	Every 4 Weeks	Every 8 Weeks	Every 12 Weeks	Every 24 Weeks		
Clinic (C) or Remote (R) Visit ^{a)}	C	C or R	C	C or R	C ^{g)}	C or R	C	C	C	C	C	
Pulse oximetry ^{d)}	X	X ^{h)}	X	X ^{h)}								
CGADR ^{p)}	X	X ^{h)}	X	X ^{h)}	X ^{h)}							
Cognitive Testing												
Computerized cognitive battery and HVLTR-R ^{j)}			X						X		X	
Clinical Laboratory Tests												
HbA1c ^{q)}	X									X		
Hematology and chemistry ^{j)}	X								X		X	
Urinalysis ^{j)}	X								X		X	
Urine drug screen ^{j)}	X								X			
Alcohol breath test ^{j)}	X											
Urine pregnancy test ^{j)} (only for females of child bearing potential)	X						X				X	
Medical Resource Utilization												
HRUQ ^{l)}	X			X								
Ongoing Subject Review												

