- l) Note for subjects whose point of entry for 54135419TRD3008 is the Optimization/maintenance phase, the survey should be completed during or shortly after Visit 2.4, or if a subject completed this visit prior to when the survey becomes available, the subject should complete the survey at the earliest possible opportunity or at early withdrawal. The survey should be administered predose (if/when performed on intranasal dosing days). Subjects who completed the Patient Stated-choice Preference survey while enrolled in a prior study (ESKETINTRD3001, ESKETINTRD3002, ESKETINTRD3003, ESKETINTRD3004, or ESKETINTRD3005) should not be issued the survey. See Section 9.5.1 in the protocol.
- m) Postdose vital signs (if/when performed on intranasal dosing days) will be performed at t = +40 minutes, and 1 hours postdose. Please refer to Section 6.1 for guidance for blood pressure monitoring on intranasal dosing days.
- n) 12-lead electrocardiogram will be performed predose at Visit 2.1 only, and at t= 1 hours postdose only for all other time points. A time window of ±15 minutes is permitted.
- o) The MOAA/S will be performed every 15 minutes from predose to t = 1 hours postdose (please refer to Section 9.2 for further guidance on MOAA/S assessments).
- p) CGADR to be performed at 30 mins; if the response is not “Yes”, the assessment will be repeated every 15 minutes until a “Yes” response is achieved or until the subject is referred for appropriate medical care if clinically indicated. On all intranasal treatment session days, subjects must remain at the clinical site until study procedures have been completed and the subject is ready for discharge.
- q) HbA1c to be performed only in those subjects with a documented medical history of diabetes
- r) Administration of the QLDS will be limited to sites where there are translations available in the local language(s)
- s) The study procedures required at a weekly frequency are only associated with an intranasal treatment session day (ie, clinic visit).
- t) Subjects entering this phase from the induction phase of this study (54135419TRD3008) will be able to reduce the frequency of intranasal treatment sessions to weekly during Weeks 1 to 4 and subsequently (after Week 4) individualize and stabilize the treatment session frequency to weekly, every other week, or every 4 weeks based on the severity of depression during this phase (see Section 3.2.2).

ABBREVIATIONS

ARC	Anticipated Event Review Committee

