2.1.2. Endpoints

Safety endpoints are listed below.

- Occurrence of TEAEs, including TEAEs of special interest
- Potential short-term effects observed on the day of intranasal treatment session with special attention to changes from baseline/predose over time for:
 - Blood pressure (systolic and diastolic) and heart rate
 - Blood oxygen saturation
 - 12-lead electrocardiogram
 - Alertness and sedation using Modified Observer's Assessment of Alertness/Sedation (MOAA/S)
- Long-term effects, with special attention to changes from baseline over time for:
 - Computerized cognitive battery and Hopkins Verbal Learning Test-Revised (HVLT-R), to assess potential effects on cognitive function
 - Columbia-Suicide Severity Rating Scale (C-SSRS), to assess potential effects on suicidal ideation and behavior
- Changes from baseline over time in clinical laboratory tests, including hematology, serum chemistry, and urinalysis
- Time to discharge readiness, using the Clinical Global Assessment of Discharge Readiness (CGADR)

Efficacy endpoints include changes from baseline over time for the following:

- Depressive symptoms, including response ($\geq 50\%$ improvement from baseline) and remission (MADRS total score ≤ 12 , PHQ-9 total score < 5); using the Montgomery Asberg Depression Rating scale (MADRS) and 9-item self-reported Patient Health Questionnaire (PHQ-9)
- Overall severity of illness, using the Clinical Global Impression Severity (CGI-S)

- Functioning and associated disability, using the Sheehan Disability Scale (SDS)
- Health related quality of life and health status, using the European Quality of Life (EuroQol) Group, 5-Dimension, 5-Level (EQ-5D-5L)
- Health related quality of life using the Quality of Life in Depression Scale (QLDS)

Exploratory endpoints include:

- Changes from baseline over time for:
 - Depression response and remission rates (as defined above) to a second induction phase in eligible subjects who had relapsed in study ESKETINTRD3003, assessed using the MADRS and PHQ-9
 - Subject treatment satisfaction
- Subject tradeoff preferences for key benefit and harm outcomes associated with TRD treatment, using a stated-choice preference survey

Refer to Section 9, Study Evaluations for evaluations related to endpoints.

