2.2. Baseline and End Point

Baseline is defined for each parameter/assessment.

- Study Baseline: For subjects who enter the study at the induction phase, the last observation prior to or on the start date of induction phase is denoted as 'Baseline'; for subjects who directly enter the study at the optimization/maintenance phase, the last observation prior to or on the start date of optimization/maintenance phase is denoted as 'Baseline'.
- Baseline (OP/MA): The last observation prior to or on the start date of the optimization/maintenance phase is denoted as 'Baseline (OP/MA)'.

Note:

- The 'Study Baseline' value is used to describe the change from baseline in the safety analysis unless otherwise specified.
- For subjects who enter the study at the induction phase, the 'Baseline (IND)' value is used for the efficacy analysis for the induction phase.; for subjects who enter the optimization/maintenance phase, the 'Baseline (OP/MA)' is used for the efficacy analysis for the optimization/maintenance phase.

For each variable measured over time, the 'End Point (IND)' value is defined as the last postbaseline assessment value during the induction phase for subjects who enter the study at the induction phase.

The ‘End Point (OP/MA)’ value is defined as the last postbaseline assessment value during the optimization/maintenance phase.

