			Day 18 (IND): 40M		
			Day 18 (IND): 1H		
			Day 18 (IND): 1H30M		
		22	Day 22 (IND): Predose	21 - 23	22
			Day 22 (IND): 40M		
			Day 22 (IND): 1H		
			Day 22 (IND): 1H30M		
25	Day 25 (IND): Predose	24 to end of IND	25		
	Day 25 (IND): 40M				
	Day 25 (IND): 1H				
	Day 25 (IND): 1H30M				
IND final visit	IND final visit	End Point (IND)	Day 1 (IND): 40M to end of IND		

Table 1: Analysis Visits

Parameter	Analysis Phase	Scheduled Day ^a	Time Interval (label on output)	Time Interval ^a (Day)	Target Time Point ^a (Day)
	OP/MA i=1,2,3,...	1	Baseline (OP/MA)	≤ 1	1
			Week 1 (OP/MA): 40M		
			Week 1 (OP/MA): 1H		
		8	Week 2 (OP/MA): Predose	2 - 11	8
			Week 2 (OP/MA): 40M		
			Week 2 (OP/MA): 1H		
		15	Week 3 (OP/MA): Predose	12 - 18	15
			Week 3 (OP/MA): 40M		
			Week 3 (OP/MA): 1H		
		22	Week 4 (OP/MA): Predose	19 - 25	22
			Week 4 (OP/MA): 40M		
			Week 4 (OP/MA): 1H		
		22 + i*7	Week (4 + i*1) (OP/MA): Predose	19 + i*7 to 25 + i*7	22 + i*7
Week (4 + i*1) (OP/MA): 40M					
Week (4 + i*1) (OP/MA): 1H					
OP/MA final visit	End Point (OP/MA)	Week 1: 40M to end of OP/MA			
Weight and body mass index (BMI), Hematology and Chemistry, Urinalysis	IND	1	Baseline	≤ 1	1
		28	Day 28 (IND)	2 to end of IND	28
		IND final visit	End Point (IND)	2 to end of IND	
	OP/MA i=1,2,3,...	1	Baseline (OP/MA)	≤ 1	1
		106	Week 16 (OP/MA)	2 - 148	106
		106 + i*84	Week (16 + i*12) (OP/MA)	65 + i*84 to 148 + i*84	106 + i*84
		OP/MA final visit	End Point (OP/MA)	2 to end of OP/MA	
Electrocardiogram (ECG)	IND	1	Baseline	≤ 1 / predose	1
			Day 1 (IND): 1H		
		15	Day 15 (IND): 1H	2 - 20	15
		25	Day 25 (IND): 1H	21 to end of IND	25
	IND final visit	End Point (IND)	Day 1 (IND): 1H to end of IND		
	OP/MA i=1,2,3,...	1	Baseline (OP/MA)	≤ 1	1
			Week 1 (OP/MA): 1H		
		50	Week 8 (OP/MA): 1H	2 - 64	50
50 + i*28		Week (8 + i*4) (OP/MA): 1H	37 + i*28 to 64 + i*28	50 + i*28	

Table 1: Analysis Visits

Parameter	Analysis Phase	Scheduled Day ^a	Time Interval (label on output)	Time Interval ^a (Day)	Target Time Point ^a (Day)	
		OP/MA final visit	End Point (OP/MA)	Week 1: 1H to end of OP/MA		
Columbia-Suicide Severity Rating Scale(C-SSRS)	IND	1	Baseline	≤ 1	1	
		4	Day 4 (IND)	2 - 6	4	
		8	Day 8 (IND)	7 - 9	8	
		11	Day 11 (IND)	10 - 13	11	
		15	Day 15 (IND)	14 - 16	15	
		18	Day 18 (IND)	17 - 20	18	
		22	Day 22 (IND)	21 - 23	22	
		25	Day 25 (IND)	24 - 26	25	
		28	Day 28 (IND)	27 to end of IND	28	
	IND final visit	End Point (IND)	2 to end of IND			
	OP/MA i=1,2,3,...	1	Baseline (OP/MA)	≤ 1	1	

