6.4. Electrocardiogram

ECG variables that will be analyzed include heart rate, RR, PR interval, QRS interval, QT interval and QTc intervals. The corrected QT (QTc) intervals will include QTcB (Bazett) and QTcF (Fridericia). Baseline values are defined in Section 2.2.

The maximum postbaseline value during each treatment phase (induction and optimization/maintenance phase) will be presented separately and will be computed for each ECG parameter using data from both scheduled and unscheduled visits.

Summary tables for observed values and changes from baseline will be presented at each scheduled time point during both treatment phases (induction and optimization/maintenance phases).

The frequency of treatment-emergent abnormalities will be tabulated and presented for all treatment phases. The identification of treatment-emergent abnormal ECG values is based on the post-baseline value (a value occurring after the start of the phase) being out of range while the Baseline value (described in Section 2.2) is either missing or within the limits given in Table 5. If postbaseline ECG results are above the upper limits (abnormally high) and the Baseline value is below the lower limits (abnormally low) or missing, then the postbaseline abnormality will also be considered treatment-emergent. The same applies to the postbaseline value being below the lower limits (abnormally low) with the Baseline value being above the upper limits (abnormally high) or missing. Abnormal ranges for the HR, PR, QRS and QT intervals are given in Table 5.

Table 5: Limits for HR, PR, QRS and QT Interval Abnormality

ECG parameter	Abnormally Low	Abnormally High
HR (bpm)	≤ 50	≥ 100
PR interval (msec)	--	≥ 210
QRS interval (msec)	≤ 50	≥ 120
QT interval (msec)	≤ 200	≥ 500

Based on the maximum QTc value for each subject during a given phase (separate for each QTc correction, QTcB and QTcF) the incidence of abnormal QTc values and changes from Baseline will be summarized. Criteria for abnormal corrected QT intervals and changes from Baseline are given in Table 6 and are derived from the International Conference on Harmonization (ICH) E14 Guidance⁴ (the same criteria apply to all QT corrections).

Table 6: Criteria for Abnormal QTc Values and Changes From Baseline

Parameter	Classification	Criteria
Clinically Significant QTc Value	No	≤ 500
	Yes	> 500
QTc change from Baseline ^a	No concern	≤ 30
	Concern	> 30 – 60
	Clear concern	> 60
QTc value	Normal	≤ 450
	> 450 - 480	> 450 - ≤ 480

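### In the optimization/maintenance phase the SAP files ECGs by day rather than by time since dose, so End Point, and possibly some 1-hour rows, mix postdose and off-dose ECGs, and a Week 1 1-hour row has no scheduled ECG behind it

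*Protocol*

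**What the plan says.** **Protocol, timing.** The Time and Events Schedule for the OP/MA phase places the ECG at Visit 2.1, every 4 weeks from Week 8, and at Early Withdrawal/End of Study. Footnote n sets the timing: "12-lead electrocardiogram will be performed predose at Visit 2.1 only, and at t= 1 hours postdose only for all other time points", with a window of ±15 minutes. The treatment-session row has no mark in the exit column. In the induction phase the first visit has a matched pair: "Twelve-lead ECG will be performed predose and t=1 hour postdose at Visit 1.1".

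**Protocol, endpoint.** Section 2.1.2 puts the "12-lead electrocardiogram" under this item: "Potential short-term effects observed on the day of intranasal treatment session with special attention to changes from baseline/predose over time for". It is not in the list of long-term effects.

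**SAP, rows.** Table 1 (Section 2.3) gives the ECG a Week 1 1H row in OP/MA, then Week 8, then rows of the form "Week (8 + i*4) (OP/MA): 1H". The ECG End Point window is "Week 1: 1H to end of OP/MA". Under Section 2.2 the End Point "value is defined as the last postbaseline assessment value during the optimization/maintenance phase". For induction the Table 1 ECG baseline is marked predose; for OP/MA it is given by day only.

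**SAP, analysis.** Section 6.4: "Summary tables for observed values and changes from baseline will be presented at each scheduled time point during both treatment phases". Changes are from Study Baseline (Section 2.2).

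**The concern.** A 1-hour postdose ECG and an exit ECG taken days after the last dose describe different states. Protocol Section 1.1.2.3 reports transient heart-rate rises after dosing, in parallel with blood pressure changes that typically resolved within 2 hours. Section 1.1.2.1 puts the median time of peak concentration at 0.37 to 0.83 hours from the first spray, so a 1-hour ECG is taken soon after the peak.

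If both kinds of ECG enter the same row, the change from baseline has no single meaning. A stable acute effect would show at each scheduled visit and shrink at End Point, which could be taken for adaptation. Separately, each planned OP/MA by-visit change sets a postdose value against a predose baseline, so it combines that day's acute effect with any drift. The endpoint that the protocol names, same-day change from predose, cannot be computed after Visit 2.1, and can be computed at Visit 2.1 only if the SAP's Week 1 1H ECG exists.

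**Working it through.** The plan states no figure on this point, so there is none to reproduce. The check uses the schedule, the SAP windows and simple contrasts.

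1. **ECGs over 52 OP/MA weeks.** By footnote n: 1 predose (Visit 2.1), 12 at 1 hour postdose (Weeks 8, 12, …, 52) and 1 exit ECG. SAP Table 1 adds a Week 1 1H ECG. By footnote n alone, a direct entrant dosed weekly has seven sessions (Weeks 1 to 7) before the first postdose ECG at Week 8.

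2. **Windows.** Week 8 covers Days 2–64. Row i covers Days 37 + 28i to 64 + 28i, so i = 1 gives 65–92 and i = 2 gives 93–120. These windows leave no gap and all carry the 1H label, so every OP/MA ECG after Day 1 falls inside a 1H window by day. Two illustrative subjects:
   - Week 8 ECG on Day 50, last dose on Day 71, exit ECG on Day 75. It is the only ECG in Days 65–92 (target 50 + 28 = 78), so by day it fills the Week 12 1H row and is also End Point.
   - Week 12 ECG on Day 78, exit ECG on Day 82. The Day 78 ECG is closest to target and keeps the row; the exit ECG becomes End Point.

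3. **Drug remaining at an exit ECG.** The exit visit is within 1 week of the last dose. With the terminal half-lives of 5.86 to 9.83 hours in Protocol Section 1.1.2.1, the fraction left is 0.5^(t/half-life):
   - 24 h: 5.8% to 18.4%
   - 48 h: 0.3% to 3.4%
   - 72 h: at most 0.6%

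4. **What each contrast estimates.** Let A be the acute 1-hour effect and L any lasting shift, in the units of the ECG parameter.
   - Later 1H minus predose baseline = A + L. The pairs (10, 0), (5, 5) and (0, 10) all give 10.
   - First-day 1H minus predose = A.
   - Off-dose exit minus predose baseline = L.

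5. **Effect on End Point.** Let p be the share of subjects with no exit visit and q the share of exit visits on a dosing day with the ECG timed after the dose. Neither is in the documents; the values below are assumptions. The off-dose share is s = (1 − p)(1 − q), and mean End Point change = L + A(1 − s). With A = 10 and L = 0, the on-dose visits all show 10:

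| p | q | s | End Point change |
|---|---|---|---|
| 0 | 0 | 100% | 0 |
| 0.10 | 0.30 | 0.90 × 0.70 = 63% | 10 × 0.37 = 3.7 |
| 0.40 | 0.50 | 0.60 × 0.50 = 30% | 10 × 0.70 = 7 |

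6. **Other off-dose ECGs.** Under Protocol Table 5 a subject can move to 4-weekly dosing at Week 6, with sessions then at Weeks 10, 14, 18 and so on. ECGs are scheduled at Weeks 8, 12, 16. The two never meet, and the ±3-day visit window does not bridge two weeks. The documents do not say what happens to those ECGs.

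7. **Baseline.** SAP Section 2.2 takes the last observation before or on the phase start date. If a Week 1 1H ECG exists and the rule is read by date alone, a direct entrant's baseline could be a postdose value.

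**The case against.** The strongest reply is that the data mostly allow the acute and lasting parts to be told apart. Visit 1.1 gives a predose and 1-hour pair, already tabulated as a Day 1 row. An off-dose exit ECG against a predose baseline is like for like and estimates the lasting part. Pulse is summarised as change from predose on each dosing day (SAP Section 6.3), so an acute heart-rate effect is shown there directly. The abnormal-QTc categories use each subject's maximum in the phase, so an off-dose exit value cannot hide an earlier postdose maximum. They are produced for QTcF as well as QTcB, so a Bazett artefact from a faster heart rate would show in the comparison. An exit ECG fills a by-visit row only when it is alone in the window or nearest the target. The study is descriptive, and long-term ECG change is not a named endpoint.

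All of this stands, and it rules out two stronger readings. A reader might infer that the design makes acute and long-term ECG effects inseparable. It does not: the limit lies in the planned tables. It is tighter only for direct OP/MA entrants, and only if no 1-hour ECG is taken at Visit 2.1. A reader might also infer that End Point is mostly off-dose. The documents give no share: an exit visit may coincide with a scheduled visit, and subjects who withdraw consent need not have one.

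The reply does not reach the ECG End Point change, which still pools two kinds of ECG, or the mismatch between footnote n and the Week 1 row.

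**Conclusion.** The point holds as a fault in the analysis plan. Following the SAP as written, the OP/MA ECG End Point mixes 1-hour postdose and off-dose values in an unknown proportion, and a 1H row can hold an ECG with no dose behind it. In the illustration, a constant acute effect of 10 shows as anything from 0 to 7 at End Point; this rests on assumed exit shares and on an acute effect that is stable and gone by the exit visit. The by-visit changes combine acute effect and drift, and no planned table separates them within OP/MA. The protocol and SAP also disagree on whether a 1-hour ECG exists at the first OP/MA session. The QTc outlier categories are not shown to be affected through End Point, since they rest on the phase maximum. The point deserves correction because a reported safety result changes and the remedy is cheap.

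**What to change.** Amend SAP Table 1 and Section 6.4:

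- **(a)** Admit to the 1H rows, and to an on-dose End Point, only ECGs taken 1 hour ±15 minutes after a dose, using the recorded ECG and dose times.
- **(b)** Report exit ECGs and any other non-dosing-day ECGs in a separate off-dose row, with change from the predose baseline.
- **(c)** Reconcile the Week 1 (OP/MA) 1H row and the start of the End Point window with footnote n, and define the OP/MA ECG baseline as predose, as is done for induction.

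A postdose-to-postdose contrast is optional. It should carry the caveat that dose can change over time, so it does not isolate drift.

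The cost is SAP wording and a few table rows. Protocol Section 9.1.1 has assessment dates and times recorded, and Section 6.1 has administration details recorded. No new ECGs are needed.
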